8.3.2. Laboratory Value Summaries

Clinical laboratory tests, including hematology, serum chemistry, urinalysis, coagulation, pregnancy testing, and serology (refer to Protocol, Section 8, Table 5), will be performed for each participant during the study in accordance with study schedule of assessments. If specific safety issues arise, additional unscheduled laboratory tests/analyses may be performed at the discretion of the investigator.

All test results and associated normal ranges from central laboratories will be reported in SI units. All tests with numeric values will have a unique unit per test.

Laboratory hematology and serum chemistry parameters identified in Protocol Section 8, Table 5 will be summarized. Numeric laboratory values will be summarized descriptively in SI units, and non-numeric test values will be tabulated when necessary. In addition, box-and-whisker plots will be provided for laboratory parameters if applicable.

For test results that will be summarized with available normal ranges, the number and percentage of participants with the laboratory values being low, normal, high, and missing will be tabulated for each test and each visit.

8.4. Vital Signs

Values at each scheduled visit, change, and percentage change from baseline for vital signs, including systolic blood pressure, diastolic blood pressure, pulse, respiratory rate, and body temperature will be summarized descriptively.

Criteria for clinically notable vital sign abnormalities are defined in [Table 1](#). The abnormal values for participants exhibiting clinically notable vital sign abnormalities will be listed along with their assigned cohort. Alert vital signs are defined as an absolute value outside the defined range and percentage change greater than 25%. The abnormal values for participants exhibiting alert vital sign abnormalities will be listed.

Table 1: Criteria for Clinically Notable Vital Sign Abnormalities

Parameter	High Threshold	Low Threshold
Systolic blood pressure	> 160 mmHg	< 85 mmHg
Diastolic blood pressure	> 100 mmHg	< 40 mmHg
Pulse	> 100 bpm	< 45 bpm
Respiratory rate	> 24 breaths/min	< 8 breaths/min
Temperature	> 38°C	< 35.5°C

8.5. Electrocardiograms

Twelve-lead ECGs including PR, QRS, QT, QTcB, QTcF, and RR intervals will be obtained for each participant during the study. Change and percentage change from baseline will be calculated at each postbaseline assessment time. Descriptive statistics will be determined for each ECG parameter.

Incidences of clinically notable ECG abnormalities are defined in [Table 2](#). Participants exhibiting clinically notable ECG abnormalities will be listed with study visit and assigned treatment group. Abnormal values for subjects with alert ECG values, defined as both the absolute value and the percentage change from baseline being outside normal ranges, will be identified and listed.

Table 2: Criteria for Clinically Notable Electrocardiogram Abnormalities

Parameter	High Threshold	Low Threshold	Percent Change
PR	> 220 ms	< 75 ms	± 25%
QRS	> 120 ms	< 50 ms	± 30%
QT	> 500 ms	< 300 ms	± 25%
QTcB	> 460 ms	< 295 ms	± 25%
QTcF	> 460 ms	< 295 ms	± 25%
RR	> 1330 ms	< 600 ms	± 25%

QTcF = Fridericia correction.

9. INTERIM ANALYSES

An interim analysis will be performed when all participants have completed the Week 12 treatment period.

10. CHANGES AND MODIFICATIONS TO THE ANALYSIS PLAN

All versions of the SAP are listed in [Table 3](#).

Table 3: Statistical Analysis Plan Versions

SAP Version	Date
Original	13 SEP 2018
Amendment 1	03 MAR 2022

10.1. Changes to Protocol-Defined Analyses

A portion of the primary endpoints that relate to hemolysis factors was removed as well as a change in the range for hemoglobin. This is a change from the Protocol in order to react to the evolving regulatory interactions and more useful information from other developments in this area.

The addition of the treatment extension evaluable population is for analysis of participants who enrolled into the open-label extension period.

An interim analysis was added for when all participants have complete Week 12 treatment. This change from the Protocol was made to support publications and a possible Phase 3 development plan for CAD participants.

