f Serology includes HIV, hepatitis, anti-Streptolysin antibody, and anti-phospholipid antibody tests.

g For women of nonchildbearing potential only (ie, surgically sterile with a hysterectomy and/or bilateral oophorectomy OR postmenopausal, defined by last menstrual period > 12 months before screening and confirmed by FSH).

^h For women of childbearing potential only.

¹ Ferritin, iron, and total iron-binding capacity will be tested at screening for all participants and at Week 6 if the participant has ongoing transfusions requirements during the study.

Single ECG. At screening, in the event that a single QTcF is > 470 milliseconds for males or > 480 milliseconds for females, triplicate ECG measurements may be performed.

k Hemoglobin, haptoglobin, LDH, reticulocyte count, total bilirubin and direct/indirect bilirubin are hemolytic markers will be measured. During follow-up, these hemolytic markers should be assessed if a participant becomes symptomatic or starts new treatment; relevant biomarkers should also be included.

Plasma for PK analysis will be collected predose and 1, 2, and 4 hours postdose at Weeks 2 and 8. Predose PK will be collected at Weeks 1 and 12.

Table 2: Schedule of Assessments for the Extension Period

		Extension Period			Follow-Up	
Procedure	Protocol Section	At Least Every 8-12 Weeks in Clinic	EOT Extension Period	Month 1 + 5 days	Month 2 ± 5 days	Month 3 ± 5 days (EOS)
Prior/concomitant medications	8.1.5	X	X	X	X	X
Study drug dispensing	6.1	X				
Study drug accountability and assess compliance	6.5	X	X			
AE assessment	8.3.1	X	X	X	X	X
Prophylactic treatment for PJP	6.7.1.1	X	X	X	X	X
Hematology ^{a,b}	8.2.1	X	X	X	X	X
Hemolysis markers ^a	8.2.1	X	X	X	X	X
Serum chemistries ^a	8.3.5.1	X				

^a Performed at each site as per the standard of care for participant's condition and monitoring at the investigator's discretion. Frequency to be determined by the investigator if it is necessary to monitor any other ongoing clinical condition.

^b Hematology panel will be performed at local laboratory.

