3. OBJECTIVES AND ENDPOINTS

Objectives	Endpoints					
Primary						
To evaluate the efficacy of INCB050465 in the treatment of participants with AIHA.	• Proportion of participants attaining a CR (defined as hemoglobin >12 g/dL not attributed to transfusion effect* and the normalization of hemolytic markers) at any visit from Week 6 to Week 12.					
	 Proportion of participants attaining a PR (defined as hemoglobin 10-12 g/dL or at least ≥ 2 g/dL increase from baseline not attributed to transfusion effect and the normalization of hemolytic markers) at any visit from Week 6 to Week 12. 					
	*No transfusion effect definition: > 1 week since last transfusion.					
To evaluate the safety of INCB050465 administered as repeat doses in participants with AIHA.	Safety and tolerability will be assessed by monitoring AEs, measuring vital signs and ECGs, and conducting clinical laboratory blood and urine sample assessments.					
Secondary						
To further evaluate the efficacy of INCB050465 in the treatment of participants with AIHA.	 Proportion of participants attaining a CR during postbaseline visits. 					
	Proportion of participants attaining a PR during postbaseline visits.					
	 Proportion of participants attaining a ≥ 2 g/dL increase in hemoglobin from baseline. 					
	Mean, change, and percentage change from baseline of hemoglobin.					
	Proportion of participants requiring transfusions.					
	Proportion of participants who achieve normalization of hemolytic markers. (Hemolysis markers: hemoglobin, haptoglobin, LDH, reticulocyte count, total bilirubin, and direct/indirect bilirubin.)					
	Change of daily usage of prednisone.					
	FACIT-F sub-scale assessment.					
To evaluate the PK effects of INCB050465.	PK endpoints: C _{max} , t _{max} , C _{min} , AUC _{0-t} , and CL/F.					
To evaluate the PD effects of INCB050465.	Change from baseline in PD markers: reticulocyte count, DAT for IgG and C3b, cold agglutinin levels, haptoglobin, total bilirubin, direct/indirect bilirubin, LDH, and complement assessment (CH50, C3, and C4).					

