Amendment 4 (31 OCT 2019)

Overall Rationale for the Amendment:

The primary purpose of this amendment is to increase the number of participants in Cohort 2 (from 10 to approximately 15) and change the proportion of CAD and warm AIHA patients. These changes are based on the recommendations from the internal Safety Review Committee meeting (18 SEP 2019).

1. Section 1, Protocol Summary (Overall Design table; Figure 1: Study Design Schema); Section 2.6, Study Rationale; Section 4.1, Overall Design; Section 4.2, Overall Study Duration; Section 10.1, Sample Size Determination

Description of change: Increased the number of participants in Cohort 2 (from 10 to approximately 15) and changed the proportion of CAD and warm AIHA patients (at least 5 CAD AIHA and up to 8 wAIHA participants; the remainder can be wAIHA, CAD, or mixed-type AIHA).

Rationale for change: To confirm clinical response signal with a slightly larger patient population and allow a better evaluation of the CAD AIHA subpopulation.

Amendment 3 (01 FEB 2019)

Overall Rationale for the Amendment:

The primary purpose of this amendment is to add an extension period for participants who are receiving clinical benefit from the study treatment and to provide guidance for hematology panel collection.

1. Section 1, Protocol Summary (Figure 1, Study Design Schema and Table 2, Schedule of Assessments for the Extension Period); Section 4.1, Overall Design; Section 6.1, Study Treatment Administered; Section 8.1, Administrative and General Procedures; Section 8.1.5, Prior and Concomitant Medications and Procedures; Section 8.3, Safety Assessments; Section 8.3, Laboratory Assessments; Section 8.8, Extension Period; Section 8.9, Follow-Up

Description of change: Added an extension period for participants who are receiving clinical benefit from the study treatment per the investigator's discretion up to the time all enrolled participants complete the study.

Rationale for change: To continue to provide study treatment to participants who are receiving clinical benefit.

3. Section 2.8.1, Potential Risks of INCB050465 Based on Preclinical Safety

Description of change: Added 3- and 9-month preclinical toxicity results in rats and in dogs.

Rationale for change: To support adding an extension period for participants who are receiving clinical benefit from study treatment.

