7.2. Efficacy Parameters

A CR for a given visit is attained if the following 2 conditions are satisfied:

1. Hemoglobin ≥ 12 g/dL.
2. Last transfusion occurred > 1 week before the date of visit.

A PR for a given visit is achieved if the following 2 conditions are satisfied:

1. Hemoglobin 10-12 g/dL or ≥ 2 g/dL increase from baseline.
2. Last transfusion occurred > 1 week before the date of visit.

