2.2 Secondary Efficacy		
2.2.1	Summary of Participants Attaining a Complete Response by Visit	FAS
2.2.2	Summary of Participants Attaining a Partial Response by Visit	FAS
2.2.3	Summary of Participants Attaining a ≥ 2 g/dL Increase in Hemoglobin From Baseline	FAS
2.2.4	Summary of Hemoglobin by Visit	FAS

Table No.	Title	Population
2.2.5	Summary of Participants Requiring Transfusions	FAS
2.2.6	Summary of Participants Achieving Normalization of Hemolytic Markers by Visit	FAS
2.2.7	Summary of Daily Usage of Prednisone by Visit	FAS
2.2.8	Summary of FACIT-F Subscale by Visit	FAS
Safety		

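### The SAP dropped marker normalization from the primary CR and PR after response data had been reviewed, and no planned table shows response with hemolysis controlled at the same visit

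*SAP*

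**What the plan says.** Protocol section 3 defines the first primary endpoint as "Proportion of participants attaining a CR (defined as hemoglobin >12 g/dL not attributed to transfusion effect* and the normalization of hemolytic markers". One qualifying visit between Weeks 6 and 12 is enough. The PR definition carries the same marker condition, joined to hemoglobin between 10 and 12 g/dL or a rise of at least 2 g/dL. Protocol Table 1, footnote k, gives the marker list: "Hemoglobin, haptoglobin, LDH, reticulocyte count, total bilirubin and direct/indirect bilirubin are hemolytic markers will be measured".

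SAP 7.2 has no marker condition: "A CR for a given visit is attained if the following 2 conditions are satisfied", and the two are hemoglobin of 12 g/dL or more and a last transfusion more than 1 week before the visit. PR keeps the protocol's hemoglobin limits with the same transfusion rule.

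SAP 10.1 declares this: "A portion of the primary endpoints that relate to hemolysis factors was removed as well as a change in the range for hemoglobin". Its stated reason is regulatory interactions and developments elsewhere in the field. SAP 10.2.1 says that updating the primary endpoint definition was the main purpose of Amendment 1, dated 03 MAR 2022.

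On access to response data, Protocol 4.1 makes the opening of Cohort 2 depend on a review of Cohort 1 safety and efficacy through Week 6. Protocol 9.6 has a committee that includes the sponsor's statistician and the investigators review clinical response regularly. Protocol Appendix D says of Amendment 4: "These changes are based on the recommendations from the internal Safety Review Committee meeting (18 SEP 2019"; the rationale given there is confirmation of a clinical response signal.

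SAP Appendix A plans CR and PR in Tables 2.1.1, 2.1.2, 2.2.1 and 2.2.2. Markers appear in Table 2.2.6, "Summary of Participants Achieving Normalization of Hemolytic Markers by Visit".

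**The concern.** Hemolysis is the disease process in AIHA. Under the protocol, a responder had to show both a hemoglobin gain and normal markers. Under the SAP, hemoglobin alone is enough. Hemoglobin can rise without hemolysis being controlled, for example after the iron, folate or B12 replacement that Protocol 6.7.1.2 allows.

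The definition changed late in an open-label trial whose response data had already been reviewed. A reader will therefore want to know how far the reported rates depend on the change, and the planned summaries do not say. The Week 12 interim analysis, added by the same SAP, is meant to support publications and a possible Phase 3 plan in CAD, so these rates will be used.

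**Working it through.** The plan states no figure on this point to reproduce. The check compares definitions, dates and planned outputs, followed by simple arithmetic.

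**1. Definitions side by side**

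| | Protocol section 3 | SAP 7.2 |
|---|---|---|
| CR hemoglobin | above 12 g/dL | 12 g/dL or above |
| PR hemoglobin | 10 to 12 g/dL, or rise of at least 2 g/dL | same |
| Transfusion | more than 1 week earlier | same |
| Markers | normalized | none |

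**2. Direction.** As written, any visit that meets the protocol CR also meets the SAP CR, and likewise for PR. Each rate can only stay equal or rise. The cut-off shift acts only at exactly 12 g/dL. That value already met the PR hemoglobin criterion, so the shift adds nobody to the CR-or-PR total. If each participant is placed in the best category, it moves a PR to a CR. Removing the markers is the material change.

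**3. Dates**
- Committee meeting, 18 SEP 2019, to SAP Amendment 1, 03 MAR 2022: 897 days.
- Protocol Amendment 5, 02 NOV 2020, which still carries the marker condition, to SAP Amendment 1: 486 days.

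**4. What the planned tables can show.** Tables 2.1.1, 2.1.2, 2.2.1 and 2.2.2 can use only the SAP 7.2 definition, because the SAP contains no other. Table 2.2.6 is by visit and has no transfusion condition. The SAP does not say whether it is a composite or one row per marker. Separate tables only bound the overlap. Suppose, as an assumption, that at one visit 12 of 25 are hemoglobin responders and 9 of 25 have normal markers. The number with both lies between max(0, 12 + 9 − 25) = 0 and min(12, 9) = 9.

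**5. Size per participant.** 1/25 = 4.0 points overall, 1/10 = 10.0 in Cohort 1, 1/15 = 6.7 in Cohort 2. For illustration only: with 12 of 25 hemoglobin responders (48%), of whom 25% to 75% also have normal markers, the marker-based count is 12 × 0.25 = 3 to 12 × 0.75 = 9, or 12% to 36%.

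**6. The PR floor.** Entry hemoglobin is 7 to 10 g/dL (Protocol 5.1, criterion 4). PR starts at 10 g/dL, and one visit among Weeks 6, 8, 10 and 12 is enough. Assume no treatment effect, a stable true value μ, within-person visit SD s of 0.3 to 0.8 g/dL, and four independent visits. With p = 1 − Φ((10 − μ)/s), the chance of at least one value of 10 or more is 1 − (1 − p)⁴.

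| μ (g/dL) | s = 0.3 | s = 0.5 | s = 0.8 |
|---|---|---|---|
| 9.0 | 0.2% | 8.8% | 36% |
| 9.5 | 17.8% | 49.9% | 71.0% |
| 9.8 | 68.8% | 81.5% | 87.2% |

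If visits were perfectly correlated, the chance would fall to the single-visit p, which for μ = 9.5 is 4.8% to 26.6%. The protocol PR has the same floor but also requires normal markers; the SAP PR does not.

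**The case against.** - **Nothing is tested.** SAP 3.2 and section 7 call every efficacy analysis exploratory, with no p-values. This stands: the issue is interpretability, not type I error.
- **The change is declared, and the timing proves nothing.** A reader might infer that the response data prompted the change. The documents do not support that. SAP 10.1 gives a different reason, and Protocol Amendment 5, issued after the 2019 review, kept the marker condition. The documents do not say which definition the committee used, which Cohort 2 data had been seen by 03 MAR 2022, or whether the interim came before that date. What remains is that response data had been reviewed before the definition changed, and SAP 10.1 does not mention it.
- **Table 2.2.6 may already be a composite.** Hemoglobin is on the SAP's marker list, so a literal composite would come close to protocol CR. Even so, it would lack the transfusion condition and the any-visit window, and would not give PR.
- **The listings hold the data.** Hemoglobin, transfusion, hematology and chemistry listings are planned, and with about 25 participants the joint status can be derived by hand. This stands, so the information is not lost. It does not help someone who reads only the tables or a publication.
- **A supportive definition would not be literally the protocol's.** This stands. Neither document defines normalization, and a PR at 10 to 12 g/dL conflicts with also requiring normalized hemoglobin. The repaired definition must be labelled as such.
- **Steroids.** A reader might think that the markers would separate drug effect from steroid effect. They would not: corticosteroids treat AIHA and could normalize the markers too.

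**Conclusion.** The point holds as a reporting gap that should be closed. The primary CR and PR lost their marker condition after response data had been reviewed in an open-label trial. The effect can only be to leave the rates equal or raise them, and no planned summary shows how large it is. A reader might also infer that the hemoglobin cut-off was materially loosened; it was not, since only a value of exactly 12 g/dL is affected and the CR-or-PR total does not change.

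The true size cannot be known from the documents. The firm figures are 4, 10 and 6.7 percentage points per affected participant, assuming the planned 25, 10 and 15. The 12-of-25 example and the visit-variability table rest on assumed values and are not estimates. The statement about direction takes CR and PR as separate proportions, as SAP 7.3 lists them. If PR were reported only for participants without a CR, CR and CR-or-PR could still only stay equal or rise, but PR alone could move either way.

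**What to change.** 1. Keep the SAP 7.2 definition as primary.
2. Add supportive versions of Tables 2.1.1 and 2.1.2, overall and by cohort. Use the protocol hemoglobin limits (CR above 12 g/dL), a last transfusion more than 1 week earlier, and LDH, haptoglobin, reticulocyte count and total bilirubin all within the laboratory reference range at that same visit. Direct and indirect bilirubin need no separate rule, because Protocol Table 5 has them measured only when total bilirubin is above the upper limit.
3. Label these tables as the protocol definition with hemoglobin taken out of the marker list, and give the reason. State how a missing marker is handled, since SAP 4.1.4 imputes nothing by default.
4. State in SAP 10.1 which response data had been reviewed, and by whom, before 03 MAR 2022.

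The cost is two tables and a short SAP edit. The markers are already scheduled at Weeks 6, 8, 10 and 12; the reticulocyte check needs the local laboratories' reference ranges in the database. The sponsor must accept that the supportive rates will equal or fall below the headline rates.

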10.2. Changes to the Statistical Analysis Plan

10.2.1. Amendment 1

The primary purpose of this amendment is to update the definition of the primary endpoints. Section [2.2](#), Section [5.3.2](#), Section [6.2](#) through Section [6.4](#), Section [7.2](#), Section [7.4](#), and [Appendix A](#) have been modified to address edits made to the SAP based on Section [10.1](#).

- Section [1](#), Section [3](#), Section [3.3](#), Section [5.2](#), Section [8.3.1](#) were updated to align with Protocol Amendments 3, 4, and 5.
- Section [8.1](#) was updated to provide more details for the safety analysis.
- Section [8.2.2](#), AESIs were added in align with parsaclisib program.
- Section 4.2.1, the definition of age was removed due to date of birth cannot be collected according to the new requirement from agency and CRF was updated to collect age instead.
- Section 4.1.4, Last Available Value was removed since it is not applicable to this study.
- Other minor changes have been incorporated throughout the SAP.

APPENDIX A. PLANNED TABLES AND LISTINGS

This appendix provides a list of the planned tables and listings for the clinical study report. Standard tables will follow the conventions in the Standard Safety Tables initial version. Shells are provided for nonstandard tables. In-text tables are identical in structure and content as appendix tables, but follow a Rich Text Format.

The list of tables, listings, and the shells are to be used as guideline. Modifications of the list or shells that do not otherwise affect the nature of the analysis will not warrant an amendment to the SAP.

Tables

Table No.	Title	Population
Baseline and Demographic Characteristics		
1.1 Disposition		
1.1.1	Analysis Populations	FAS
1.1.2.1	Summary of Participant Disposition in the Treatment Period	FAS
1.1.2.1	Summary of Participant Disposition in the Extension Period	TE
1.1.3	Summary of Number of Participants Enrolled by Site	FAS
1.2 Demography		
1.2.1	Summary of Demographics	FAS
1.3 Baseline Characteristics		
1.3.1	Summary of Baseline Disease Characteristics	FAS
1.4 Prior Medication and Concomitant Medication		
1.4.1	Summary of Prior Medications	FAS
1.4.2	Summary of Prior Medications for AIHA	FAS
1.4.3	Summary of Concomitant Medications	FAS
1.5 Others		
1.5.1	Summary of General Medical History	FAS
1.5.2.1	Summary of Protocol Deviations by Category in the Treatment Period	FAS
1.5.2.2	Summary of Protocol Deviations by Category in the Extension Period	TE
Efficacy		
2.1 Primary Efficacy		
2.1.1	Summary of Participants Attaining a Complete Response at any Visit From Week 6 to Week 12	FAS
2.1.2	Summary of Participants Attaining a Partial Response at any Visit From Week 6 to Week 12	FAS
2.2 Secondary Efficacy		
2.2.1	Summary of Participants Attaining a Complete Response by Visit	FAS
2.2.2	Summary of Participants Attaining a Partial Response by Visit	FAS
2.2.3	Summary of Participants Attaining a ≥ 2 g/dL Increase in Hemoglobin From Baseline	FAS
2.2.4	Summary of Hemoglobin by Visit	FAS

Table No.	Title	Population
2.2.5	Summary of Participants Requiring Transfusions	FAS
2.2.6	Summary of Participants Achieving Normalization of Hemolytic Markers by Visit	FAS
2.2.7	Summary of Daily Usage of Prednisone by Visit	FAS
2.2.8	Summary of FACIT-F Subscale by Visit	FAS
Safety		
